15.2 Definition of secondary outcome measures

Overall survival time is defined as the interval in whole days between the date of randomisation into the trial and date of death from any cause. Patients who do not die during the course of the trial will be censored at the date when they were last known to be alive. The median survival will be reported as will the six month survival rate, both of which will be calculated using the method of Kaplan-Meier estimation.

Performance status of the patient is classified by the clinician at each treatment visit according to ECOG definitions (Oken *et al.*, 1982). The trial will assess the change over time in this measure.

AEs will be recorded according to the definitions given in Appendix 4 of the protocol with grade of events recorded by CTCAE version 4.0. Treatments will specifically be compared in terms of the number of patients who experience at least one grade 3 or grade 4 AE.

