3.3 Outcome measures

Primary:

- Progression free survival time

Secondary:

- Progression-free rate at 4 months from randomisation
- Overall survival time
- Overall survival rate at 6 months
- Changes in performance status
- Quality of life (EQ-5D)
- Adverse events (as defined by Section 10.0)

Translational:

- Biomarkers: blood and biopsy samples will be collected for analysis of PARP and DNA repair pathways.

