6.5 Follow up period

Patient follow-up will continue until 2 ½ years after the last patient has been recruited.

Patients who discontinue treatment for reasons other than progression should continue to have CT scans every 8 weeks until progression or alternatively until the follow-up period is complete.

The frequency of follow-up for patients, after the treatment phase has ended, will be at the discretion of the Investigator at the recruiting sites. It is anticipated that patients will be seen as a minimum every three months.

A Follow-up Form should be completed by the Investigator or a delegated member of the site research team and returned to the STOMP Trial Office every three months until the patient dies or the end of the follow-up period as defined above. This form will capture the date the patient was last seen in that 3 month follow-up period.

Every endeavour should be made to follow patients up in accordance with the protocol. Where patients fail to attend clinic the patient's GP should be contacted for follow-up information, patient consent permitting.

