7.1.3 Cycle 2 and all Subsequent Cycles (Day 1 of 4 Weekly Visit)

All patients will be assessed by the following methods every 4 weeks whilst receiving STOMP trial medication. All assessments should ideally be carried out on the visit date but can be carried out up to 3 days prior to the visit. Unless otherwise specified data will be collected on a cycle specific Treatment Form which will be completed at the end of the cycle of treatment to capture all data relevant to that cycle.

- Physical examination (including weight)
- ECOG performance status
- Blood pressure (supine), pulse and temperature
- Haematology (to include Hb, WBC, ANC and platelets) and clinical chemistry to include (sodium, potassium, adjusted calcium, urea, creatinine, albumin, total serum protein, total bilirubin, alkaline phosphatase, AST/ALT)

STOMP Protocol

- APTT and INR recommended for patients on warfarin (see Section 6.2)
- AE review. Complete an Adverse Event Monitoring Form capturing all AEs suffered during the previous cycle (i.e. Cycle 1 Adverse Event Monitoring Form is completed on day 1 of Cycle 2 and so on)
- Concomitant medication review. Complete a Concomitant Medication Log capturing the concomitant medication taken during the previous cycle (i.e. Cycle 1 Concomitant Medication Log is completed on day 1 of Cycle 2 and so on)

In addition:

- The patient should be given the relevant Patient Diary and the previous cycle's diary should be collected and returned to STOMP Trial Office
- The patient should be asked to complete a Quality of Life questionnaire. The site research team should ensure that the date the questionnaire was completed and the time point (the cycle 1 questionnaire is completed at the cycle 2 day 1 visit and so on) are appropriately recorded on the Quality of Life Compliance Form before returning to the STOMP Trial Office. Please note if a quality of life assessment is missed for any reason the Quality of Life Compliance Form should still be returned to document the fact that the assessment was not performed
- Blood samples for biomarker, and if applicable CTC analysis, should be taken 28 days after commencing treatment (or day 1 of cycle 2) only. See Section 9 and the separate Translational Study Guidelines

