7.1.6 Treatment Discontinuation (28 Days Post-completion of Treatment)

For patients who discontinue treatment the following assessments should be carried out approximately 28 days after taking their last dose of trial medication:

- Haematology (to include Hb, WBC, ANC and platelets) and clinical chemistry to include (sodium, potassium, adjusted calcium, urea, creatinine, albumin, total serum protein, total bilirubin, alkaline phosphatase, AST/ALT)
- AE review. Complete an Adverse Event Monitoring Form
- Concomitant medication review. Complete a Concomitant Medication Log[‡]

STOMP Protocol

In addition:

- The patient should be asked to complete a Quality of Life questionnaire. The site research team should ensure that the date the questionnaire was completed and the time point (in this instance this will be the End of Treatment Assessment) are appropriately recorded on the Quality of Life Compliance Form before returning to the STOMP Trial Office. Please note if a quality of life assessment is missed for any reason the Quality of Life Compliance Form should still be returned to document the fact that the assessment was not performed.
- Blood samples for biomarker, and if applicable CTC analysis should be taken. See Section 9 and the separate Translational Study Guidelines[†]

[≠] If the patient commences second line therapy before the treatment discontinuation assessment is due please provide data up until the commencement of second line therapy

[†] If the patient has progressed and is to commence second line therapy please ensure samples are taken prior to commencing second line treatment

Patients who discontinue treatment for reasons other than progression should continue to have CT scans every 8 weeks until progression, or alternatively until the follow-up period of the trial is complete. Patients who discontinue for progression should be managed in accordance with Section 7.2.

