7.1.7 Follow-up Assessments

Patient should be followed up as detailed in Section 6.5. A Follow-up Form should be completed every 3 months for all patients following discontinuation of treatment (unless patient has withdrawn consent for future data transfer). Patients who discontinue treatment for reasons other than progression should continue to have CT scans every 8 weeks until progression, or alternatively until the follow-up period of the trial is complete. A Response Form should therefore be completed every 8 weeks for these patients.

Archival tumour tissue samples will be requested retrospectively during the follow-up period (see Section 9).

STOMP Protocol

Table 7.1 Schema of trial assessments

	Screening (Day -28 to 0)	Pre-cycle 1 (Day -7 to treatment commence- ment)	Cycle 2 and all subsequent cycles (Day 1 of 4 weekly visit)	End of odd cycles ⁱ	End of even cycles ^j	Treatment dis- continuation (28 days post completion of treatment)	Follow- up ^l
Informed consent	X						
Medical history	X						
Review of Inclusion/exclusion criteria	X						
Peripheral blood smear to test for MDS & AML (if clinically indicated)	X						
Physical examination	X	X	X				
Vital signs, body weight (includes BP, pulse and temperature) Height only at screening	X	X	X				
ECOG performance status	X	X	X				
Haematology ^a / clinical chemistry ^b	X	X	X			X	
Pregnancy test ^c	X						
Coagulation tests (if clinically indicated) ^{d+e}	X		X				
Blood sample for biomarker analysis & CTC		X	X ^h			X	
Tumour Assessment (CT according to RECIST)	X				X ^k		X ^m
Chest X-ray ^f		X		X			
Patient Diary		X	X				
Quality of Life Questionnaire (EQ- 5D-3L)		X	X			X	
Adverse Events	X		X			X	
Concomitant medications	X		X			X	
Randomisation (day 0 only)	X						
Olaparib/placebo dispensed/returned		X ^g	X				
Archival tumour sample (when available)							X
Survival							X

a Haematology to include Hb, WBC, ANC, platelets.

b Clinical chemistry to include calculated or measured creatinine clearance, AST/ALT and total bilirubin at screening and sodium, potassium, adjusted calcium, urea, creatinine, albumin, total serum protein, total bilirubin, alkaline phosphatase, AST/ALT at all other time points.

c For female patients of child-bearing potential as defined in Section 6.4.1.

d Coagulation test to include INR and APTT.

STOMP Protocol

- e Recommended during treatment if patient is receiving warfarin, measured weekly for first month and monthly thereafter.

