15.4 Methods for analysis

All analyses will be carried out on an intention-to-treat basis. Median progression-free survival time and overall survival time will be reported using Kaplan-Meier estimates together with 90% confidence intervals. In addition the survival rates at 4 and 6 months will be estimated and provided with 90% confidence intervals. Progression-free survival will be compared for each treatment arm to the pooled control group using the log-rank test.

In addition to the log-rank test, analysis of PFS using a Cox proportional hazards model will be considered. This analysis of PFS will adjust for prognostic factors in addition to the trial stratification factors. These factors may include stage and performance status at diagnosis. Consideration will also be given to the use of an interval censored data approach to the analysis of PFS.

Once 105 PFS events have been observed then there will also be an interim assessment of overall survival. A further analysis of overall survival will be performed after a further 6 months of follow up.

Changes in performance status over time will be assessed using longitudinal methods of analysis and will account for informative dropout. AEs, as a whole, will be reported as the number of patients on each treatment arm experiencing each event at each grade. In particular, the difference in the number of patients experiencing at least one grade 3 or grade 4 AE will be estimated with a 95% confidence interval.

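### ECOG performance status is scheduled only while patients are on trial drug, so the promised adjustment for informative dropout has no off-treatment values to support it

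*Protocol*

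**What the plan says.** Section 3.3 of the protocol lists "Changes in performance status" among the secondary outcomes. Section 15.2 fixes when it is measured: "Performance status of the patient is classified by the clinician at each treatment visit". Section 15.4 puts all analyses on an intention-to-treat basis and adds: "Changes in performance status over time will be assessed using longitudinal methods of analysis and will account for informative dropout".

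The schedule matches 15.2 but goes no further:

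- **Baseline.** Performance status is taken at screening (7.1.1) and before cycle 1 (7.1.2).
- **On treatment.** Section 7.1.3, which includes performance status, opens: "All patients will be assessed by the following methods every 4 weeks whilst receiving STOMP trial medication".
- **Discontinuation.** Section 7.1.6 says that "the following assessments should be carried out approximately 28 days after taking their last dose of trial medication". It then lists blood tests, adverse events, concomitant medication, the quality-of-life questionnaire and biomarker samples. Performance status is not listed.
- **Follow-up.** Section 6.5 says of the 3-monthly Follow-up Form: "This form will capture the date the patient was last seen in that 3 month follow-up period". It does not mention performance status.
- **Table 7.1.** The row "ECOG performance status" is marked at screening, pre-cycle 1 and cycle 2 onwards. It is blank at treatment discontinuation and at follow-up.

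Trial treatment stops at progression (7.2).

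**The concern.** Performance status can be expected to worsen around progression, and that is when the schedule stops recording it. If olaparib preserves function by delaying progression, much of the contrast between arms lies in values that nobody is asked to record.

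Most of this is not dropout in the usual sense. Patients who stop trial drug stay under follow-up, with a form due every three months. They are still seen, but the outcome is no longer measured. If the drug works as hypothesised, recording also stops earlier on control than on olaparib, so the missing data are tied to the primary outcome and unequal between arms.

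A statistical analysis plan can choose a model for this, but it cannot supply observations that the schedule does not collect.

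**Working it through.** **Step 1: is any off-treatment value scheduled?** Sections 6.5, 7.1.6 and 7.1.7 and the last two columns of Table 7.1 contain none. Section 7.2 refers to 7.1.5 for assessments at discontinuation; that section covers CT scans and does not list performance status either. Section 7.4.2 keeps patients who withdraw from treatment only under protocol assessment, but the schedule holds no off-treatment performance status for them to have.

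**Step 2: the planning inputs.** The protocol gives no figure for this outcome, so the size is taken from its PFS assumptions in 15.3: median 4.8 months on control, 7.8 months on olaparib, 75 patients per arm. As a check that these medians underlie the design, the event formula with HR = 4.8/7.8 = 0.615, one-sided 5%, 80% power and 1:1 allocation gives

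4 × (1.645 + 0.842)² / (ln 0.615)² ≈ 105 events,

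which is the stated figure.

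**Step 3: share with no further scheduled value.** Assume exponential PFS and treatment stopping only at progression or death. The share at time t is 1 − exp(−ln 2 × t / median). The 4- and 6-month points are the ones that 3.3 uses for its rate outcomes.

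| Months | Control (4.8) | Olaparib (7.8) | Difference | Still observed, of 75 |
|---|---|---|---|---|
| 4 | 1 − 0.561 = 44% | 1 − 0.701 = 30% | 14 points | 42 v 53 |
| 6 | 1 − 0.420 = 58% | 1 − 0.587 = 41% | 17 points | 32 v 44 |
| 12 | 1 − 0.177 = 82% | 1 − 0.344 = 66% | 17 points | 13 v 26 |

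**Step 4: records per patient.** Two years of 4-weekly cycles allow at most 25 post-baseline records (day 1 of cycles 2 to 26). With q the probability of remaining progression-free over 28 days, the expected number is the sum of q^k for k = 1 to 25: about 6.8 on control and 10.2 on olaparib.

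**Step 5: what these figures omit.** PFS events include deaths (15.1), so some of the missing values could never be collected. In the other direction, stops for toxicity or by choice end recording before progression and would raise both shares.

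**The case against.** The strongest reply is that the protocol is consistent and already aware of the problem. Section 15.2 defines an outcome at treatment visits and 7.1.3 schedules exactly that. Section 15.4 names informative dropout and undertakes to deal with it; the choice of model can be left to the analysis plan. On-treatment function is a reasonable outcome for a phase II maintenance trial, since values after progression would mix the effect of trial drug with that of second-line treatment. The quality-of-life questionnaire is collected at the discontinuation visit, and delay of progression is measured by the primary outcome. Follow-up visits are at the investigator's discretion, so later values would be patchy.

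Much of this stands, and it limits the point to a secondary outcome. It does not remove it. An on-treatment outcome is defensible, but 15.4 does not describe one: it promises intention to treat with an allowance for dropout. With no off-treatment value from any patient, that allowance is extrapolation.

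Two stronger readings are tempting and are not supported:

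- A reader might infer that the arms are compared only among patients who have not progressed. Section 15.4 plans no such restriction, and patients who later progress contribute all their earlier records. The observed set is also those still on treatment, which is different: patients who stop for other reasons are lost too, and 7.3 allows treatment to continue while progression is in doubt, with the progression date then set back to the initial scan.
- A reader might convert the gap between arms into an unobserved difference in ECOG grade. The documents give no figure for the fall at progression, and the calculation would count deaths as values that could have been collected.

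**Conclusion.** The gap is real and is one of data collection. Performance status ends with trial treatment, while the planned analysis implies a course over time in all randomised patients. At 6 months roughly 58% of control and 41% of olaparib patients would have no further scheduled value. This rests on exponential PFS at the protocol's medians, with stopping only at progression or death. The shares include deaths, and earlier stops for other reasons would raise them.

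The bias in the performance-status comparison cannot be sized from the documents. The primary analysis is unaffected. The case for change rests on the low cost and on the fact that the values cannot be recovered once a contact has passed.

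**What to change.** 1. Add ECOG performance status to the 28-day discontinuation visit: section 7.1.6, the matching column of Table 7.1, and the Treatment Discontinuation Form.
2. Add it to the 3-monthly Follow-up Form, to be completed where the patient is seen.
3. Extend 15.2 beyond treatment visits, and state in 15.4 that the longitudinal analysis covers all randomised patients, uses these values and handles death explicitly. Appendix 2 scores death as ECOG grade 5, so the text should say whether that score enters the analysis.

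The cost is one extra item on two existing forms plus the schedule change. No new visit is needed: the 28-day contact already includes adverse-event review and the questionnaire, and 6.5 anticipates that patients are seen at least every three months. Some follow-up values will be missing, particularly where information comes through the GP, and later values will reflect second-line treatment. The dropout problem is therefore reduced rather than removed.

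If the sponsor prefers not to collect these values, 15.2 and 15.4 should describe the outcome as on-treatment performance status, so that no intention-to-treat statement is made about the period after stopping.

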7.1.1 Screening (day -28 to 0, i.e. Randomisation Date)

The following assessments should be performed to assess eligibility during the screening period:

- Medical history including AE review (from time of consent) and concomitant medication review
- Physical examination (including height and weight) to assess fitness and ECOG performance status
- Blood pressure (supine), pulse and temperature
- The following tests should be conducted to confirm patient eligibility:
 - Hb
 - WBC
 - ANC
 - Platelet count
 - Calculated or measured creatinine clearance
 - AST/ALT
 - Total bilirubin
- Coagulation tests (APTT and INR) if clinically indicated (unless the patient is receiving warfarin)
- Peripheral blood smear to test for MDS and AML (if clinically indicated)
- Pregnancy test for female patients of child-bearing potential (see Section 6.4.1)

STOMP Protocol

- CT chest and upper abdomen (to include liver and adrenals) performed in accordance with RECIST 1.1 (see Appendix 3)
- Final confirmation of eligibility (at point of randomisation)

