10.1 Reporting requirements

10.1.1 Adverse Events

All medical occurrences which meet the definition of an AE (see Appendix 4 for definition) should be reported with the exception of abnormal laboratory findings for which only abnormal laboratory findings of \geq grade 3 will be reported.

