10.2 Reporting Period

Details of all AEs (except those listed above) will be documented and reported from the date that the patient is consented into the trial until 28 days after the administration of the last dose of trial medication.

SAEs that are judged to be at least possibly related to trial treatment must still be reported in an expedited manner irrespective of how long after IMP administration the reaction occurred.

STOMP Protocol

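### The named safety comparison counts grade 3 or 4 AEs only and is by intention to treat: a fatal-only event counts as none, never-dosed patients enter, and pre-dose events can enter

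*Protocol*

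**What the plan says.** Protocol 15.2, on secondary outcome measures: "Treatments will specifically be compared in terms of the number of patients who experience at least one grade 3 or grade 4 AE". Protocol 15.4 gives the matching analysis: "the difference in the number of patients experiencing at least one grade 3 or grade 4 AE will be estimated with a 95% confidence interval". Neither section mentions grade 5 or says 'or higher'.

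Section 15.4 also sets the population, with no exception for safety: "All analyses will be carried out on an intention-to-treat basis".

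On timing, Section 10.2 has AEs recorded "from the date that the patient is consented into the trial until 28 days after the administration of the last dose of trial medication", and the screening list in 7.1.1 agrees: "Medical history including AE review (from time of consent) and concomitant medication review". Section 3.3 lists adverse events as a secondary outcome and defines them by reference to Section 10.0. Section 15.2 refers instead to Appendix 4, which describes events in a person given a medicinal product.

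For the wider AE tables, 15.4 states: "AEs, as a whole, will be reported as the number of patients on each treatment arm experiencing each event at each grade". Section 10.1.1, however, makes an exception for "abnormal laboratory findings for which only abnormal laboratory findings of" grade 3 and above are reported.

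**The concern.** Safety is part of the trial's aim (3.1) and of its secondary hypothesis (3.2). The grade 3-4 count is the only AE comparison for which 15.4 promises a confidence interval, so it is the number most likely to be quoted as the safety result. Three features of the wording weaken it:

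- The worst grade is outside the count, so a patient who dies of an AE with no other severe event is classed with patients who had no severe event.
- The intention-to-treat rule keeps in the denominator patients who could not have had a drug effect.
- Nothing in 15.2 or 15.4 keeps out events that arose after consent but before the first tablet, some of which may be due to the preceding chemotherapy.

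The second and third features pull the difference towards zero. In a safety comparison that is the reassuring direction.

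**Working it through.** The protocol gives no rate, power or sample size for this comparison, so there is no figure to reproduce. The check sets the sections side by side and then illustrates size.

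**1. Can a fatal event be on file as grade 5 alone?** Section 10.3.1.1 records, for each sign or symptom, only the highest grade since the last visit. Section 10.4 requires the AE behind a death that is not clearly due to progression to be reported. So a fatal sepsis, for example, can be recorded as grade 5 with no grade 3 or 4 entry. The patient then fails the 15.2 definition unless another event, or an earlier visit, was grade 3 or 4.

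Size: 15.3 plans 75 patients per arm. One such patient moves the arm's rate by 1/75 = 1.3 points; three in one arm move it by 3/75 = 4.0 points.

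**2. Can a pre-dose event be counted?**
- Screening opens 28 days before randomisation (7.1.1), and treatment should start within 3 days of randomisation (6.3). If consent is taken when screening opens, it precedes first dose by up to 28 + 3 = 31 days.
- First dose is at most 42 days after day 1 of the last chemotherapy cycle (6.1). With first dose at that limit, consent can fall 42 - 31 = 11 to 42 - 28 = 14 days after day 1 of that cycle, and earlier if treatment starts sooner.
- Inclusion criterion 5 (5.2.1) requires chemotherapy toxicity, except alopecia, to be grade 1 or better at entry. That excludes ongoing grade 3-4 toxicity. It does not erase an event that arose after consent and then resolved.

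**3. Dilution by pre-dose events.** Let p be the share of each arm with a counted pre-dose event, independent of later risk, and r the on-treatment rate. The observed rate is p + (1 - p)r, so the difference is (1 - p)(r_T - r_C). The 95% half-width is 1.96 × √(q_C(1 - q_C)/75 + q_T(1 - q_T)/75), where q is the observed rate. Power is the usual two-proportion value at two-sided 5%. Assumed rates are 20% v 40%:

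| p (assumed) | Observed rates | Difference (points) | Half-width (points) | Power |
|---|---|---|---|---|
| 0% | 20% v 40% | 20 | 14.3 | 77% |
| 5% | 24% v 43% | 19 | 14.8 | 70% |
| 10% | 28% v 46% | 18 | 15.2 | 63% |
| 20% | 36% v 52% | 16 | 15.7 | 51% |

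**4. Dilution by never-dosed patients.** If a share u of each arm is never dosed and has no counted event, the difference becomes (1 - u)(r_T - r_C). For the same rates, u = 2% gives 19.6 points and u = 5% gives 19.0. Both values of u are assumptions.

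**5. Laboratory grades.** Section 1.4 describes the anaemia and neutropenia seen with olaparib as mainly grade 1-2. Under 10.1.1 laboratory findings of those grades are not reported as AEs, yet 15.4 promises every event at every grade. Haematology is measured each cycle (7.1.3), so the grades could be derived.

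**The case against.** The strongest reply is that little is lost and much is settled elsewhere. The by-grade table in 15.4 includes grade 5, 10.4 covers deaths, the DMC reviews all SAEs (10.3.2.3), and overall survival is a secondary outcome. This stands. A reader might infer that fatal events vanish from the safety reporting; they do not. They are missing from one summary count, the one with the confidence interval.

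Second, 10.2 is a collection period. Sections 15.2 and 15.4 give no window for the comparison, and a treatment-emergent rule is commonly left to the SAP. This also stands in part. A reader might infer that the comparison is defined to run from consent and so counts chemotherapy toxicity. The protocol does not say that, and criterion 5 bars ongoing toxicity above grade 1. What remains is narrower: 3.3 ties the AE outcome to Section 10.0, whose period opens at consent, while 15.2 points to Appendix 4, which leans towards events on the drug. Pre-dose events can be counted, and the two references do not settle it.

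Third, pre-randomisation events are balanced in expectation and favour neither arm. Correct: the effect is dilution. Treatment is also expected within 3 days of randomisation, so never-dosed patients may be few.

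Fourth, the laboratory threshold cannot alter a grade 3-4 count, and the 15.4 table can be read as covering only reported AEs. Both are fair, so that is a secondary point.

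**Conclusion.** Two rules are wrong as written, and both are fixed in the protocol: the grade wording in 15.2 and 15.4 leaves out grade 5, and the intention-to-treat rule in 15.4 covers safety without exception. A third weakness, that pre-dose events can enter the count, follows from reading 3.3 with 10.2. It is a possibility, not a stated rule.

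The firm size is 1.3 points per fatal-only patient in an arm of 75. The direction of that effect on the comparison is unknown, because it depends on which arm such patients fall in. The dilution factors (1 - p) and (1 - u) are exact under the assumptions stated, but p, u and the 20% v 40% rates are not in the documents. The table shows what dilution would do, not what to expect.

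It would go too far to call the comparison blind to death, or biased in favour of one arm by earlier chemotherapy. The primary analysis and the sample size are untouched.

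**What to change.** In 15.2 and 15.4, define the comparison as the number of patients with at least one AE of grade 3 or higher (3, 4 or 5) that starts or worsens from first dose to 28 days after last dose, among patients who took at least one dose, by treatment received. Limit the intention-to-treat sentence in 15.4 to the efficacy analyses. State how deaths clearly due to progression (10.4) are handled, so that widening to grade 5 does not bring in disease deaths. Align 3.3 and 15.2 on a single AE definition.

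List pre-dose events separately from the baseline AE form (Table 11.1). That form is completed at randomisation, so events in the days between randomisation and first dose need an onset date to be placed correctly.

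For the by-grade table, either say that it covers reported AEs only, or derive CTCAE grades for haemoglobin, neutrophils, white cells and platelets from the values taken each cycle.

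The cost is wording in 3.3, 15.2 and 15.4 and some programming. The AE forms and haematology values are already collected.

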10.3 Reporting procedure

10.3.1 Site

10.3.1.1 Adverse Events

AEs should be reported on an AE Form (and where applicable on an SAE Form). An AE Form should be completed at each visit and returned to the STOMP Trial Office.

AEs will be reviewed using the CTCAE, version 4.0 (see Appendix 5). Any AEs experienced by the patient but not included in the CTCAE should be graded by an Investigator and recorded on the AE Form using a scale of (1) mild, (2) moderate or (3) severe. For each sign/symptom, the highest grade observed since the last visit should be recorded.

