10.4 Deaths

All deaths that occur during the trial, or within 28 days after the administration of the last dose of trial medication, must be reported as follows:

Death clearly the result of disease progression should be documented on a Death Form but should not be reported as a SAE.

Where death is not due (or not clearly due) to progression of the disease under study, the AE causing the death must be reported as a SAE within **24h**. The report should contain a comment regarding the co-involvement of progression of disease, if appropriate, and should assign main and contributory causes of death. This information can be captured on the Death Form.

Deaths with an unknown cause should always be reported as a SAE. A post mortem maybe helpful in the assessment of the cause of death and, if performed, a copy of the post-mortem results should be forwarded to the STOMP Trial Office within the usual timeframes.

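### The grade 3 or grade 4 cut-off in the one AE comparison with a confidence interval leaves out a patient whose only severe AE record is fatal (grade 5)

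*Protocol*

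**What the plan says.** Section 15.2 sets the scale, "with grade of events recorded by CTCAE version 4.0", and names the comparison: "Treatments will specifically be compared in terms of the number of patients who experience at least one grade 3 or grade 4 AE". Section 15.4 gives the method: "the difference in the number of patients experiencing at least one grade 3 or grade 4 AE will be estimated with a 95% confidence interval". Neither section says grade 3 or higher or mentions grade 5. All other AE reporting in section 15.4 is descriptive: "AEs, as a whole, will be reported as the number of patients on each treatment arm experiencing each event at each grade".

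Section 10.3.1.1 governs the AE Form completed at each visit: "For each sign/symptom, the highest grade observed since the last visit should be recorded". Visits on treatment are every 4 weeks (sections 4.1 and 7.1.3). Under section 10.4, when a death is not clearly due to progression, "the AE causing the death must be reported as a SAE". Deaths clearly due to progression go on a Death Form and are not SAEs.

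**The concern.** A severe-toxicity count normally includes the most severe outcome. Here the cut-off has an upper limit as well as a lower one, so the worst outcome falls outside it. The omission has a direction: each patient whose only severe record is fatal lowers the severe-AE count of that patient's arm.

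Safety is part of the trial's aim (section 3.1) and of its secondary hypothesis (section 3.2), and this is the one AE contrast that will carry an estimate and an interval. Both statistical sections use the same words, so this is the stated definition and not a slip in one place. A SAP that follows the protocol would inherit it.

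**Working it through.** The protocol gives no expected AE rate, power or precision for this comparison, so there is no planned figure to reproduce. The design figures in section 15.3 concern PFS and do not bear on the point, apart from the arm size.

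**Inputs**
- Event: at least one AE of grade 3 or 4 (sections 15.2 and 15.4).
- Scale: CTCAE v4.0 (sections 10.3.1.1 and 15.2). Appendix 5 refers to the scale without printing it. That grade 5 means death is a property of the adopted scale and is taken as an assumption.
- Arm size: 75 (section 15.3).
- AE counts: not given; assumed below.

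**Step 1: who is left out**

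| Record of a patient with a fatal AE | In the count? |
|---|---|
| Another AE recorded at grade 3 or 4 | Yes |
| Same AE recorded at grade 3 or 4 at an earlier visit | Yes |
| Same AE graded 3 or 4 on an SAE Form before death | Can be; the protocol does not say which forms feed the count |
| Only severe record is grade 5 | No |

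Only the last row is lost. It arises when an event begins and becomes fatal with no grade 3 or 4 report in between. The highest-grade rule then leaves a single entry for that event on the AE Form, at the fatal grade.

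**Step 2: weight of one patient**

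1/75 = 0.0133, or 1.3 percentage points of an arm. With k_T such patients on an olaparib arm and k_C on placebo, the estimated difference is too low by (k_T − k_C)/75. Equal numbers leave the difference unchanged.

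**Step 3: effect on the interval, with assumed counts**

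Wald interval: d ± 1.96 × √[p_T(1 − p_T)/75 + p_C(1 − p_C)/75], where d = p_T − p_C. For 30 v 20 patients: p_T = 0.400, p_C = 0.267, d = 0.133, SE = √(0.00320 + 0.00261) = 0.0762, giving 13.3 points (−1.6 to 28.3).

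| Grade 3–4 base, olaparib v placebo | Fatal-only patients added | Difference, points (95% CI) |
|---|---|---|
| 30 v 20 | none | 13.3 (−1.6 to 28.3) |
| 30 v 20 | 1 v 0 | 14.7 (−0.3 to 29.6) |
| 30 v 20 | 2 v 0 | 16.0 (1.0 to 31.0) |
| 30 v 20 | 3 v 0 | 17.3 (2.3 to 32.4) |
| 25 v 15 | none | 13.3 (−0.7 to 27.3) |
| 25 v 15 | 1 v 0 | 14.7 (0.6 to 28.7) |
| 25 v 15 | 3 v 1 | 16.0 (1.7 to 30.3) |

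**Step 4: how much depends on the assumed base**

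Both bases lie close to the point where the lower limit meets zero. With 20 placebo patients and 3 v 0 fatal-only patients added, the lower limit crosses zero only if the olaparib base is 29, 30 or 31. At 28 it moves from −4.2 to −0.3 and stays below zero. At 32 it is already 1.0 before anything is added. The shift in the estimate is the same for every base; a changed reading of the interval is confined to a narrow window.

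**The case against.** The strongest reply is that few patients can be affected and that fatal AEs are visible elsewhere. Much of this stands.

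- An event that is life-threatening or leads to unplanned admission is an SAE (Appendix 4). It must be reported within 24 hours of awareness with severity by CTCAE (section 10.3.1.2), and later information goes on a new form (section 10.3.1.3). A grade 3 or 4 phase may therefore be documented before death. A reader might infer that every fatal AE drops out of the count; the documents do not support that.
- Fatal AEs appear in the by-grade table (section 15.4) and in SAE reporting (section 10.4), and the DMC reviews all SAEs (section 10.3.2.3). Deaths also enter PFS and overall survival (sections 15.1 and 15.2). A reader might infer that fatal toxicity is hidden; it is not. But the by-grade table carries no between-arm estimate, and PFS and overall survival mix toxic deaths with disease deaths, so none of these replaces the contrast.
- A reader might infer an uneven rule, because AEs outside CTCAE are graded "using a scale of (1) mild, (2) moderate or (3) severe", so that a fatal one would be counted at grade 3. This is doubtful: that scale is set out for the AE Form, while a death not clearly due to progression needs an SAE report, whose severity is documented by CTCAE.
- A reader might infer from section 1.4 that fatal toxicity is already known. That section mentions pneumonitis in a small number of patients, mostly low-grade cytopenias and some grade 3–4 thrombocytopenia, but no fatal event.
- No decision rule depends on the interval excluding zero; section 15.4 only estimates the difference.

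None of this changes the literal definition: a patient whose only severe record is grade 5 contributes nothing to the count.

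**Conclusion.** The point holds in a limited form and is minor. As written, the one AE comparison with a confidence interval leaves out patients whose only severe AE record is grade 5, and so understates severe toxicity in the arm with more of them, by 1.3 percentage points of an arm per patient. This rests on the CTCAE convention that a fatal AE is grade 5 and on the planned 75 per arm. The number of such patients cannot be derived from the protocol and may be small or zero. It would be tempting to conclude that two or three fatal events decide the safety result; that is true only for assumed counts near the boundary and is not supported in general. The primary endpoint, sample size, error rates and safety reporting are unaffected.

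**What to change.** In sections 15.2 and 15.4, change the event from a grade 3 or grade 4 AE to an AE of grade 3 or higher (grades 3 to 5). State that deaths clearly due to disease progression remain outside, as in section 10.4. Under this definition a patient counts whether a severe event was last recorded at grade 3, 4 or 5, so it no longer matters whether an earlier grade was captured on an SAE Form.

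The cost is one phrase in two sections, best changed before unblinding. It needs no new data, because section 10.4 already requires the AEs behind deaths not clearly due to progression to be reported, and no change to visits or sample size. The by-grade table in section 15.4 already shows grade 5 separately.
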